## 2.4 Gradient- and Spin-Echo DSC perfusion imaging

The relative cerebral blood volume (rCBV), derived from dynamic susceptibility contrast magnetic resonance imaging (DSC-MRI), is an established biomarker of glioma status that can aid in diagnosis, detecting treatment response, guiding biopsies, and reliable differentiation of post-treatment radiation effects and tumor progression. It is also increasingly leveraged as a biomarker of early therapeutic response in clinical trials. A gradient-echo (GE) echo-planar imaging (EPI) sequence is commonly applied dynamically every 1-1.5 s, during which gadolinium-based contrast agent is injected as a bolus, and the T2\*-weighted images are used to calculate tumor blood volume (BV) maps.

The GE-EPI is more commonly used for DSC-MRI because it has high sensitivity to the susceptibility effect caused by the contrast agent. However, it also causes more susceptibility artifact in areas with tissue interface, hemorrhage and is more subject to the susceptibility-blooming near large vessels. When these factors are of concern, spin-echo (SE) EPI can be applied for DSC-MRI as an alternative approach in the clinic, despite its reduced overall sensitivity. In addition to their differences in overall sensitivity, it is well-known that GE-EPI is more sensitive to relaxivity changes caused by contrast agents in larger vessels whereas SE-EPI is more specific to those in vessels with size in the capillary level. When both GE and SE images are acquired following a bolus injection of contrast agent, a vessel size map can be constructed. The voxel value in the vessel size map represents mean vessel caliber of the voxel, which may serve as a useful surrogate for characterizing tumor angiogenesis and monitoring treatment-related changes.

## 2.5 Chemical Exchange Saturation Transfer (CEST) MRI

Chemical exchange saturation transfer (CEST) is a promising new MRI contrast mechanism that has been used in studying the tumor microenvironment through the detection of mobile proteins and peptides. This technique relies on the labeling of endogenous populations of exchanging protons by a radiofrequency pulse at a specific frequency. These pools can transfer their magnetization to the unbound water (through the exchange), the extent of which constitutes the MRI image contrast, and by varying the radiofrequency pulse frequency, a spectrum is generated. In the absence of the CEST effect, this spectrum is generally considered to be symmetric; however, in its presence, the signal is attenuated at specific frequencies, resulting in chemical-specific negative peaks. Two CEST effects apparent *in vivo* are attributed to protons of mobile proteins: backbone amide signals with their base catalyzed proton transfer (APT), and Nuclear Overhauser enhancement (NOE) mediated aliphatic proton magnetization transfer (so-called exchange-relayed NOE).

# Proprietary Information of MD Anderson

Protocol No: 2019-1008

Version No: 04

Version Date: August 31, 2021

MRI based on the chemical exchange saturation transfer (CEST) effect from amine, amide, sulfhydryl and hydroxyl protons associated with endogenous metabolites has been shown to provide imaging maps of metabolites in tissue noninvasively. Amide proton transfer (APT) imaging has been developed, which detects amide protons of low concentration in endogenous proteins and peptides in tissue. APT has shown promising results in differentiating radiation necrosis from tumor progression in glioma and necrosis models in rats. APT has also been applied to human glioma patients to differentiate high-grade tumors from low-grade ones with encouraging results. Most germane to this project, the NOE immediately surrounding a brain metastasis one-week following treatment with stereotactic radiosurgery was shown to significantly correlate with tumor volume change at one-month post-treatment. Thus, CEST imaging appears to be a promising tool to help inform future treatment decisions in patients with brain metastasis.

To overcome the limitations of endogenous CEST-MRI techniques, exogenous molecules have been exploited as extracellular tumor pH reporters for CEST-MRI applications. In the last decade, most work has focused on FDA-approved iodinated contrast agents, considering their high safety profile and translational potential. Due to their hydrophilic chemical structure, iodinated agents remain confined outside the cells and can be visualized as perfusion agents in tumor by CEST-MRI. One of the main advantages of using FDA-approved iodinated contrast agents is their very high safety profile for administration in patients. Consequently, CEST-MRI pH imaging with iopamidol was initially translated for measuring kidney and bladder pH in healthy volunteers. Later on, the capability to provide accurate tumor pH maps was demonstrated with iopamidol in both breast and ovarian cancer patients showing acidic tumor pH values. Their first application as pH CEST-MRI agents involved the use of iopamidol (Isovue®, Bracco Diagnostic), which possesses two amide proton pools that can be saturated at 4.2 and 5.5 ppm. The set-up of a ratiometric procedure allows to accurately measure extracellular tissue pH (pHe) in the pH range of 5.5–7.9, independently of the contrast agent concentration, with an accuracy of 0.1 units at several magnetic fields. CEST-MRI tumor pH imaging was combined to FDG-PET to elucidate the deregulation of tumor metabolism in a breast cancer model. This work evidenced that tumor regions with more acidic pHe show increased FDG uptake and demonstrated in vivo, for the first time, the relationship between tumor acidosis and high glycolytic rate. The combination of CEST pH-imaging and FDG-PET was then exploited for predicting the early therapeutic efficacy of metformin in a preclinical model of pancreatic cancer. In addition, the possibility to measure tumor pHe opened new routes for monitoring the effect of novel anticancer treatments that can reverse the glycolytic tumor phenotype.

Based on this prior work, [name] (MDACC) has invented and implemented a clinical imaging method that evaluates tumor acidosis, known as “acidoCEST MRI”. Chemical Exchange Saturation Transfer (CEST) MRI is used to detect the two pH- dependent CEST signals of a clinically approved contrast agent (iopamidol), and we have developed advanced analysis methods that use these CEST signals to measure the extracellular pH (pHe). Our pre-clinical studies have shown that an early response to treatment can cause a change in pHe.

## 2.6 Multiple inversion time (TI) arterial spin labeling (ASL) “Adv ASL” perfusion imaging

Arterial spin labeling (ASL) is an MRI technique that can noninvasively and quantitatively determine cerebral blood flow (CBF) by magnetically labeling the arterial water spins with radiofrequency pulses. This method takes advantage of the fact that water protons of the arterial blood in the feeding vasculature of the brain are magnetically labeled and used as an endogenous tracer. After a specific inversion time, the labeled blood arrives at the image plane in which the image is acquired. In clinical studies, it has been used to assess perfusion in neurodegenerative diseases, epilepsy, central nervous system neoplasms, and vascular malformations. However, a disadvantage of ASL-MRI is that in patients with cerebrovascular disease, the quantification of CBF is hampered by the recruitment of additional blood flow through collateral pathways. These alternative pathways of blood flow lead to delayed arrival of the labeled blood bolus to the brain.

As most ASL-MRI techniques acquire the labeled images at a fixed time after the initial labeling of arterial blood, it is possible that the magnetic label may not have reached the imaging plane, leading to underestimation of CBF. Previous studies reported that tumor-brain blood flow ratios determined by arterial spin-labeling were markedly higher than those obtained with dynamic susceptibility-weighted contrast-enhanced MR imaging. This is probably caused by the underestimation of perfusion in brain regions with long arterial transit times. The use of higher inversion times would overcome these limitations; however, this would conversely lead to a decrease in the SNR caused by the rapid decay of the ASL perfusion signal over time. Recently, ASL-MRI with the acquisition of a series of images at multiple delay times after the initial labeling has been introduced as a method to compensate for these issues and also demonstrated the ability to differentiate low-grade and high-grade astrocytomas.

## 2.7 Protocol Particular Disease Description

Brain metastasis will be defined as a three-dimensional intraaxial enhancing abnormality on MR imaging in a patient with pathology-proven extracranial non-central nervous system malignancy.

# 3 ELIGIBILITY

## 3.1 Inclusion Criteria

- An adult patient with pathology-proven solid organ cancer.
- MRI of the brain with contrast, positive for at least one intra-axial metastatic lesion greater than 5 mm.
- Planned treatment with stereotactic radiation.

## 3.2 Exclusion Criteria

- Contraindication to MR imaging.

# Proprietary Information of MD Anderson

Protocol No: 2019-1008

Version No: 04

Version Date: August 31, 2021

- Known allergy to gadolinium-based contrast agents.
- Renal failure as defined by a GFR less than 30 or the use of hemodialysis.
- Pregnant.
- Patients less than 18 years of age will be excluded.

## 3.3 NUMBER OF PARTICIPANTS

Fifty (50) patients will be studied.

## 4 STUDY PLAN/DESIGN

### 4.1 Patient Enrollment:

Patients scheduled to undergo brain radiation at MD Anderson Cancer Center will be screened for eligibility based on their screening diagnostic MRI scan and available clinical information. Once eligibility is confirmed, patients will be approached for protocol introduction and consenting and enrollment. Enrolled patients will undergo the **baseline** study MRI scan with contrast within the fourteen (14) days before their scheduled brain radiation treatment.

### 4.2 Procedure to Obtain Consent

The patients will be approached by either the Diagnostic Imaging faculty or Research Staff, including research nurses and research coordinators for their approval before their procedure. During the consenting process, patients will be educated and consented for their research participants in this study.

### 4.3 MR Scanning:

The study MRI will be performed on a 3.0-T MRI system. All patients will undergo conventional anatomic MR imaging including 3D T1 pre and post-contrast weighted imaging, dynamic contrast-enhanced perfusion imaging, magnetic resonance spectroscopic imaging, as well as the study specific sequences to include:

- Quantitative MRI
- CEST
- Adv Diff
- GESE DSC
- Adv ASL

# Proprietary Information of MD Anderson

Protocol No: 2019-1008

Version No: 04

Version Date: August 31, 2021

The study sequences will add approximately thirty (30) minutes to the conventional imaging sequences with the entire scan time to be less than sixty (60) minutes which adheres to a standard UTMDACC MR Operations scanning appointment time slot.

## 4.4 Contrast Administration

- 4.4.1 Iodinated contrast for acidoCEST imaging: Up to 120 mL of iopamidol using weight based MDACC scale.
  - 4.4.1.1 Patients with history of allergy or adverse reaction to iodinated contrast will not receive iodinated contrast or acidoCEST imaging. They will receive APT CEST imaging only.
- 4.4.2 Gadolinium-based contrast: Gadolinium dosing will be performed per MDACC standard-of-care protocol for advanced brain tumor imaging including a unit dose preceding DCE perfusion imaging and a second unit dose preceding DSC perfusion imaging.
- 4.4.2.1 Patients with history of allergy to gadolinium-based contrast will be excluded from enrollment per section 3.2 of the protocol (Exclusion criteria).

## 4.5 Imaging Time Points

- 4.5.1 The baseline study scan will be performed within the fourteen (14) days **before** scheduled brain radiation treatment.
- 4.5.2 Seven additional study scans will be performed on the schedule of the patient's clinical protocol, but not less than four (4) weeks apart and not more than 16 (sixteen) weeks apart.

## 4.6 Conclusion of Study Participation:

- 4.6.1 Completion of eight (8) study scans.
- 4.6.2 Upon patient request.
- 4.6.3 A contraindication to further MR imaging.
- 4.6.4 Death.

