# Proprietary Information of MD Anderson

Protocol No: 2019-1008

Version No: 04

Version Date: August 31, 2021

Disease **recurrence** will be determined by surgical pathology (if available) or at least three months of imaging follow-up. Imaging findings will be considered recurrent disease in a lesion if:

1. The lesion was originally considered to be a treatment responder.
2. The lesion showed a successive increase in the size of 25% from nadir or a single imaging time point increase of 40%. (see section 5.1)

Lesions that show an increase in size, but do not meet these criteria will be considered radiation necrosis.

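### A responding lesion first seen to grow by 25% to under 40% at its last available scan is labelled radiation necrosis only because imaging stopped; section 7.1 has no class for unresolved growth.

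*Combined protocol and SAP*

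**What the plan says.** Section 4.5 sets a baseline scan in the 14 days before radiation, and then "Seven additional study scans will be performed on the schedule of the patient's clinical protocol", spaced "not less than four (4) weeks apart and not more than 16 (sixteen) weeks apart". Section 4.6 ends participation on "Completion of eight (8) study scans", and also on patient request, a contraindication to further MR, or death. Follow-up is therefore set by a number of scans, not by a length of time.

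Section 7.1 gives the reference label for growth after treatment: "Disease recurrence will be determined by surgical pathology (if available) or at least three months of imaging follow-up". Within the imaging route, two conditions must hold. The lesion must first have responded, and it must then grow, either by a successive 25% from nadir or by 40% at one scan. The remainder is assigned by default: "Lesions that show an increase in size, but do not meet these criteria will be considered radiation necrosis". There is no third class.

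Section 7.3 uses the label in a Wilcoxon rank-sum comparison of CNR between lesions with treatment change and lesions with progressive disease. I take treatment change there to mean the radiation necrosis label of section 7.1. Secondary objectives 1.2.2.2 to 1.2.2.5 concern this distinction.

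**The concern.** The default sentence treats two situations alike. In one, growth was watched further and did not go on to meet the criteria. In the other, growth was seen once and nobody looked again. The first is evidence bearing on the label; the second is absence of evidence. Because participation stops at a scan count or at an early exit, some lesions may fall in the second situation, and the plan records them as necrosis.

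Ending imaging can move unconfirmed progression into the necrosis group, but it cannot create a successive increase and so cannot move necrosis into the progression group. If CNR truly differs between the two conditions, this mixing tends to hide the difference that the objectives are meant to find. The label also comes to depend partly on when a patient's scans ran out.

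**Working it through.** **Plan's own figure.** The plan states no follow-up duration, so there is none to reproduce. Its one precision figure (14.5 points, section 7.2) belongs to the primary baseline endpoint and does not enter here.

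**Step 1: length of study imaging.** Inputs from sections 4.5 and 4.6: eight scans, hence seven intervals of 4 to 16 weeks, applying the spacing limits to the first interval as well.
- Shortest: 7 × 4 = 28 weeks from the baseline scan.
- Longest: 7 × 16 = 112 weeks.
- The baseline scan may precede radiation by up to 2 weeks, so at the shortest spacing the last scan falls 28 − 2 = 26 to 28 weeks after treatment.

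**Step 2: the growth criteria at the last scan.** Take a responder whose first growth appears at its last available scan, with no pathology.
- 40% or more: meets the single-scan rule, so the size criterion for recurrence is satisfied.
- 25% to under 40%, for example 30%: below the single-scan rule. A successive increase needs a further scan, and there is no further study scan. The default gives radiation necrosis.

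This holds at every permitted spacing, because it depends on the order of scans and not on weeks. It applies at scan 8, and equally at the last scan before an early exit.

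**Step 3: the three-month condition.** Section 7.1 does not say when the three months start, so both readings are shown.

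*Reading A: from first regrowth, study scans only.* With spacing g weeks, the imaging left after scan k is (8 − k) × g weeks. Response can first be seen at scan 2, so regrowth can first be seen at scans 3 to 8, which is six positions. Three months is taken as 13 weeks, or alternatively 12.

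| g (weeks) | Weeks left after scans 3, 4, 5, 6, 7, 8 | Positions short of 13 weeks | Positions short of 12 weeks |
|---|---|---|---|
| 4 | 20, 16, 12, 8, 4, 0 | 4 (scans 5–8) | 3 (scans 6–8) |
| 8 | 40, 32, 24, 16, 8, 0 | 2 (scans 7–8) | 2 (scans 7–8) |
| 12 | 60, 48, 36, 24, 12, 0 | 2 (scans 7–8) | 1 (scan 8) |
| 16 | 80, 64, 48, 32, 16, 0 | 1 (scan 8) | 1 (scan 8) |

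So 1 to 4 of 6 positions fall short at 13 weeks, and 1 to 3 at 12 weeks.

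*Reading B: from treatment.* A patient who completes eight scans has at least 26 weeks, which exceeds 13. The count is 0 of 6.

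**Step 4: what these counts mean.** They are scan positions, not lesions. Nor are they counts of mislabelled lesions: at 4-week spacing, growth first seen at scans 5, 6 or 7 still has three, two or one later study scans on which a successive increase could appear. For a patient who completes, the only position with no later study scan is scan 8.

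**The case against.** Ending participation after a fixed number of scans is an ordinary design choice, and section 4.6 is not itself at fault. The problem lies in the default and the missing class in section 7.1. That stands, and the fix is aimed there.

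A reader might infer that regrowth first seen late cannot be judged at all. The documents do not support this. A 40% increase at the last scan meets the size criterion on that scan alone, and pathology can settle a case of any size. A reader might also take three months of imaging as an alternative to successive growth. In section 7.1 it is the alternative to pathology, and the growth thresholds apply within the imaging route. Finally, a reader might treat 1 to 4 of 6 scans as the size of the misclassification. That count assumes a clock starting at first regrowth, which section 7.1 does not state, and no sentence says that falling short of three months by itself makes a lesion necrosis.

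It can also be said that section 7.1 confines neither the imaging nor the pathology to the participation period, and that section 4.5 ties scans to the clinical schedule. The investigators may therefore intend to use later clinical data. Nothing bars it, but nothing provides for it either, and the label should not rest on an unstated intention.

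The consequence is limited: only secondary comparisons are touched, without multiplicity adjustment, and the plan acknowledges that the overall error rate exceeds 5%.

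**Conclusion.** The concern holds in a narrow form. A responder with first growth of 25% to under 40% at its last available scan, and without pathology, is assigned to radiation necrosis because observation ended. This rests on only study scans entering the label, since the plan provides for nothing else. Some of these lesions will truly be necrosis; the plan has no means of telling which.

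The error goes in one direction and enters the necrosis-versus-progression comparison. How many of the 50 patients' lesions are affected cannot be derived, because the documents give no regrowth rate, timing or drop-out rate. The primary analysis at baseline is unaffected.

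Separately, the undefined start of the three months leaves the imaging route open to readings under which 0 to 4 of 6 possible regrowth scans fall short in patients who complete. Correcting both is a cheap improvement.

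**What to change.** Amend section 7.1, with a cross-reference from section 4.6:

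1. State when the three months of imaging follow-up start.
2. State that routine clinical post-contrast MRI and any surgical pathology obtained after the last study scan count towards the label, with consent for record review.
3. Class as indeterminate, and leave out of the main necrosis-versus-progression test, growing responders that have no pathology, have not met the 40% rule, and have no later imaging on which a successive increase could be judged. A lesion that has already met the 40% rule keeps its classification.
4. Add a sensitivity analysis that keeps the current default of necrosis for the indeterminate lesions, because leaving them out is itself a selection. Report their number.

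No study scan is added. The cost is protocol wording, some record review, the loss of a few lesions from the main test, and a final analysis that may wait up to about three months longer.

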## 5 Image Analysis

### 5.1 Metastasis size evaluation:

- 5.1.1 A patient must have a single enhancing intraaxial brain metastasis of 5 mm or greater for study inclusion.
- 5.1.2 Metastases will be measured on axial T1 post-contrast imaging on a slice displaying the maximal tumor size using the longest diameter after appropriate magnification on the picture archiving and communicating system (PACS) monitors.
- 5.1.3 Only metastasis planned for radiation therapy will be assessed (for example, lesions present at baseline imaging that are planned for surgical resection will not be assessed).
- 5.1.4 For patients with more than one metastasis appropriate for study assessment, up to ten (10) lesions will be assessed.
  - 5.1.4.1 If there are more than ten lesions present, the five most caudal (lowest) and the five most cranial (highest) lesions that meet evaluation criteria will be tracked.

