# **7 STATISTICAL CONSIDERATIONS**

## **7.1 Definitions**

Brain metastases “**treatment response**” will be defined by size and contrast to noise ratio (CNR).

Size – treatment response in a lesion will be considered as a decrease in size of 30%. (see section 5.1)

CNR—treatment response will be considered as a decrease in T1 post-contrast CNR of at least 20% (see section 5.2) by standard T1 post contrast imaging for a lesion.

Metastases that do not meet these criteria for treatment response will be considered treatment failure.

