## 7.2 Sample Size

For each of the primary conspicuity endpoints, the objective is to estimate the ability of each imaging method (T2 weighted MRI, CEST MRI, Adv Diff, and DESE DSC) at identifying brain metastases at baseline. Standard of care qualitative T1 post-contrast imaging will be considered the gold standard. Each patient will have between 1 and 10 lesions, with an expected average of 4 lesions per patient. (For patients with more than 10 lesions, 10 will be chosen as described in Section 5.1.4.1.) The primary analysis will consider the largest lesion within each patient, and the analysis will be repeated considering all lesions. The sensitivity will be calculated along with the corresponding 95% confidence interval. With 50 patients, this confidence interval will be no wider than 14.5% on either side of the estimated proportion. The confidence interval around the proportion of total lesions detected will be tighter, depending on the total number of lesions.

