## 7.3 Analysis Plan

Patients are expected to have on average four brain lesions each. The primary analysis will be performed on the largest lesion within patients at baseline, and secondary analyses will consider all lesions. The sensitivity of each method at detecting lesions as determined by T1 weighting will be reported with 95% confidence intervals. Analyses will also be performed at the subsequent scans as numbers permit.

For the secondary endpoints that consider treatment response, for each of the imaging methods, at each time point, we will calculate the contrast to noise ratio (CNR) in patients with lesions that respond to treatment and in patients with local failure and will compare these by using a Wilcoxon rank-sum test. If numbers permit, analyses may be repeated using all lesions. Additionally, of the lesions that initially respond, some will subsequently grow in size after the initial response. Of these, some will be considered treatment change and some residual disease. The CNR will be compared between lesions with treatment change and those that are progressive disease using a Wilcoxon rank-sum test.

All statistical tests will be performed with two-sided tests with 5% Type I error rates. No adjustment will be made for the multiplicity of testing. We recognize that the Type I error rate overall will be greater than 5%.

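### Lesions stay in response scoring after later local treatment, so a treatment failure can be counted as a responder in the secondary analyses; previous radiation to a study lesion is also not addressed

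*Combined protocol and SAP*

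**What the plan says.** **Selection.** Section 3.1 requires "Planned treatment with stereotactic radiation", and 4.1 adds that "Patients scheduled to undergo brain radiation at MD Anderson Cancer Center will be screened for eligibility". The exclusions in 3.2 are MR contraindication, gadolinium allergy, renal failure, pregnancy and age under 18. At lesion level, 5.1.3 states "Only metastasis planned for radiation therapy will be assessed" and removes lesions with resection planned at baseline. All five treatment-response objectives in 1.2.2 concern stereotactic radiosurgery.

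**Reference.** Section 2.7 reads "Brain metastasis will be defined as a three-dimensional intraaxial enhancing abnormality on MR imaging", in a patient with proven extracranial cancer. Section 7.2 takes T1 post-contrast imaging as the reference for baseline sensitivity.

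**Follow-up.** Section 4.5.2 plans seven further scans, 4 to 16 weeks apart. Under 4.6, participation ends at eight scans, patient request, MR contraindication or death.

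**Scoring.** Section 7.1 says "treatment response in a lesion will be considered as a decrease in size of 30" percent, and also counts a fall of at least 20% in T1 post-contrast CNR as response. Lesions that do not qualify are failures. Recurrence rests on pathology where available, otherwise on at least three months of imaging. On imaging it needs an earlier response plus growth of 25% from nadir or 40% at one time point. Growth short of these thresholds is called radiation necrosis.

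**Analysis.** Section 7.3 compares CNR between responders and local failures at each time point, and between treatment change and progression, by Wilcoxon rank-sum test: "All statistical tests will be performed with two-sided tests with 5% Type I error rates".

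**The concern.** The response label is meant to describe what the study radiosurgery did to the lesion. Nothing in the plan ties the label to that treatment. If a lesion is irradiated again, falls within a whole-brain field or is operated on, later scans show the effect of the second treatment and are scored by the same rules.

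Two things are at stake, both in the secondary analyses. First, true failures can move into the responder group. This mixes the groups and depletes the smaller one. Second, the error can carry forward. Imaging recurrence requires a prior response and is measured from nadir, so a response produced by later treatment makes a lesion eligible for recurrence and lowers the value that growth is measured against.

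A related gap lies at entry. A lesion irradiated before the study, enhancing again and booked for further radiation, meets every stated criterion and can be a patient's index (largest) lesion. The reader of the results could not tell how many such lesions there were.

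**Working it through.** **1. Is later local treatment within the follow-up window?** Seven intervals of 4 weeks give 7 × 4 = 28 weeks, and of 16 weeks 7 × 16 = 112 weeks. Section 7.1 itself foresees surgical pathology. Section 5.1.3 covers only resection planned at baseline.

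**2. What do the rules do with such a lesion?** An invented example:
- 20 mm at baseline, 19 mm at follow-up: a 5% decrease, so failure on size.
- After further local treatment it measures 14 mm: (20 − 14)/20 = 30%, so the size criterion for response is met.
- The nadir is now 14 mm, not 19 mm. Growth to 18 mm is 4/14 = 28.6%, above the 25% threshold, although 18 mm is below the earlier nadir.
- Growth to 16 mm is 2/14 = 14.3%, below threshold, so the default label is necrosis.

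Section 7.1 does not say plainly whether the size and CNR criteria must both be met. The gap exists on either reading.

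**3. What could mislabelling cost?** The documents give no failure rate, effect size or rate of later treatment. Assumed: 50 patients with one lesion each, F true failures, true AUC 0.75, and a share r of failures relabelled as responders while keeping failure-like CNR.
- Contamination of the responder group: w = rF / (50 − F + rF).
- Observed AUC: A = (1 − w) × 0.75 + w × 0.5.
- Noether approximation: power = Φ(|A − 0.5| × √(12 c(1 − c) × 50) − 1.96), with c = F(1 − r)/50.

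For F = 10 and r = 0: 0.25 × √(12 × 0.16 × 50) − 1.96 = 0.49, so power is 69%.

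| F | r | failures left | w | A | power |
|---|---|---|---|---|---|
| 10 | 25% | 7.5 | 0.059 | 0.735 | 54% |
| 10 | 50% | 5 | 0.111 | 0.722 | 37% |
| 10 | 75% | 2.5 | 0.158 | 0.711 | 20% |
| 5 | 50% | 2.5 | 0.053 | 0.737 | 24% (from 45%) |
| 15 | 50% | 7.5 | 0.176 | 0.706 | 44% (from 80%) |

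Fractional counts are expectations, and the approximation is rough with so few failures. Most of the loss comes from the shrinking failure group, not from the fall in AUC.

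**4. Baseline precision and previous radiation.** Section 3.3 says "Fifty (50) patients will be studied" and 7.2 says "With 50 patients, this confidence interval will be no wider than 14.5% on either side of the estimated proportion". The exact (Clopper-Pearson) interval at 25/50 is 35.5% to 64.5%, a half-width of 14.47 points, which reproduces the stated figure. If previously irradiated index lesions were dropped without replacement, the half-width near 50% would be 14.8 points (5% dropped, n = 48), 15.3 (10%, n = 45) or 16.2 (20%, n = 40). Replacing such patients at entry keeps 14.5.

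To see how far results with and without such lesions could differ, let f be the share of index lesions that are old necrosis, and assume a method positive in 90% of other lesions and 30% of necrotic ones. Observed sensitivity is (1 − f) × 0.90 + f × 0.30, which gives 87%, 84% and 78% for f = 5%, 10% and 20%. With 80% in place of 90%, and 30% to 50% in necrosis, it is 77.5–78.5%, 75–77% and 70–74%. All these inputs are assumptions, and the direction depends on how each sequence shows necrosis.

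**The case against.** No sentence in the plan says that a later scan overwrites an earlier failure label, and the recurrence rule speaks of lesions that responded originally. A sensible analyst might therefore fix the label early. That is fair, but 7.1 gives no assessment time and 7.3 forms response groups at each time point, so the text permits either course.

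Three stronger readings are tempting and are not supported:
- *A reader might infer that old necrosis biases the primary estimate.* No passage limits the baseline target to untreated lesions. Sections 1.1, 7.2 and 7.3 set the target as metastases seen on T1, so a missed enhancing lesion is a miss by the plan's own definition. The route is also narrow: the lesion must be the largest assessed, previously irradiated, planned for radiation again, and not viable tumour. Shifts of 3 or 6 points (90% to 87% or 84%) lie inside the 14.5-point half-width.
- *A reader might infer that a resected failure becomes a responder with complete shrinkage.* Pathology can settle recurrence under 7.1, and a fully removed lesion leaves no lesion ROI for CNR under 5.2. What stands is that 7.1 does not say how its size response is scored afterwards. Resection is the weaker part; repeat and whole-brain radiation are the stronger.
- *A reader might infer from 2.1 that advanced imaging cannot separate necrosis from progression.* The sentence on difficulty concerns ADC. For perfusion imaging, 2.1 reports improved accuracy, with sensitivity and specificity below 90%.

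Two further limits stand. The affected tests are secondary and openly unadjusted for multiplicity. Systemic therapy can also change lesion size, and the rule proposed here does not address it.

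**Conclusion.** The main point holds. Sections 4.6, 5.1.3 and 7.1 allow a lesion to go on being scored for response, nadir and recurrence after later local treatment, so the stated rules can turn a failure into a responder in the secondary Wilcoxon comparisons. This part does not affect the primary baseline sensitivity. Its size is unknown; the power losses above illustrate assumed failure counts, AUC and relabelling rates and are not predictions.

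The previous-radiation gap is a true omission of lesser weight. It calls for recording and a sensitivity analysis. It does not show that the primary estimate is wrong.

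The treatment wording also needs reconciling: 5.1.3 refers to radiation therapy in general, 3.1 to stereotactic radiation and 1.2.2 to radiosurgery. Since 3.1 already requires planned stereotactic radiation for every patient, the practical reach is limited to additional lesions treated differently in the same patient.

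**What to change.** **In 7.1, as an analysis rule only, with no bearing on care:**
- A lesion's last evaluable scan is the one before any repeat radiation to it, whole-brain radiation or resection of it.
- Response or failure status and nadir are fixed from scans up to that point.
- Recurrence versus necrosis is taken from pathology if the lesion is resected.
- A lesion given later local treatment before three months of imaging follow-up, without pathology, is labelled indeterminate and left out of the necrosis-versus-progression comparison. Without this clause, closing follow-up early would push undecided lesions into the default necrosis label. The text should also say when the three months begin.

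**For previous radiation:** record it per lesion, and report baseline sensitivity and the treatment-response analyses with and without such lesions. If the sponsor prefers to exclude them in 5.1.3, then 3.1 must require at least one unirradiated lesion. Otherwise patients can enrol with nothing to assess, and n = 50 with its 14.5-point precision is lost.

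**Wording:** reconcile 5.1.3 with 3.1 and 1.2.2.

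**Cost:** a short amendment and a per-lesion field for dates of local treatment. Section 6.1 mentions collecting dates but does not establish that these are captured. Some later scans and a few indeterminate lesions leave the secondary analyses. The 7.1 rule leaves the primary sample size unchanged.
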